5.2.2. Clinical Response Analysis Set

The clinical response analysis set consists of the patients in the safety analysis set in whom clinical response (assessed by the investigator) has been evaluated. Patients who meet any of the following criteria will be excluded:

- i. Information on clinical response assessment is not reported at all (description in the report, “no clinical response information”)
- j. Non-target disease of the study (description in the report, “Non-target disease of the study”) [That is, “others” is checked with no other information in the CRF item that asks the disease (diagnosis) that required the use of AMEPAROMO.]

5.3. Subgroups

Subgroup analyses of safety will be performed for the following patient background factors. Underlined categories will be used as a reference in comparisons between subgroups.

- Sex [male, female]
- Children (<15 years), adults (≥15 to <65 years), elderly (≥65 years)
- Inpatient/outpatient status at the first prescription [inpatient, outpatient]
- Diagnostic name [intestinal amebiasis, others]
- Severity [mild, moderate, severe, unknown]
- Initial onset/recurrence [initial onset, recurrence]
- HIV infection [absent, present]
- Past medical history other than HIV infection [absent, present]
- Concurrent illness other than HIV infection [absent, present]
- Presence or absence of prior treatment for intestinal amebiasis [absent, present]
- Presence or absence of hepatic dysfunction [absent, present]
- Presence or absence of renal dysfunction [absent, present]
- Presence or absence of concomitant medication up to the development of adverse drug reactions^a [absent, present]

Subgroup analyses of safety will be performed for the other factors shown below.

- Pregnant and parturient women (pregnancy present)

^a: The presence or absence of concomitant medications will be determined by excluding concomitant medications started to be used after the day of onset of the last adverse drug reaction observed during the observation period plus 28 days.

- Overdose^b (overdose present)

Patients in whom AMEPAROMO might have been contraindicated per the package insert (hereinafter referred to as contraindicated patients) will be sampled from the registry according to separately-specified criteria and be analyzed for the safety of AMEPAROMO as a subgroup analysis.

Subgroup analyses of effectiveness will be performed for the following patient background factors. Underlined categories will be used as a reference in comparisons between subgroups.

- Sex [male, female]
- Presence or absence of hepatic dysfunction [absent, present]
- Presence or absence of renal dysfunction [absent, present]
- Children (<15 years), adults (≥15 to <65 years), elderly (≥65 years)
- Severity [mild, moderate, severe, unknown]
- Initial onset/recurrence [initial onset, recurrence]
- HIV infection [absent, present]
- Past medical history other than HIV infection [absent, present]
- Concurrent illness other than HIV infection [absent, present]
- Presence or absence of prior treatment for intestinal amebiasis [absent, present]

Hepatic and renal dysfunction will be considered “present” if there is at least one complication falling under the following MedDRA SMQs and HLGTS. The judgment will be made using the MedDRA version at the data cutoff for periodic safety update report or the final database release because SMQs, HLGTS, etc. may be changed due to version updates.

- Hepatic dysfunction: SMQ (narrow) “hepatic disorders” and HLGT “hepatic and hepatobiliary disorders” + “hepatobiliary neoplasms”
- Renal dysfunction: SMQ (narrow) “acute renal failure” + “renal vessel disorders” + “chronic kidney diseases” and HLGT “nephropathies” + “renal disorders”

^b: Because the dosage and administration of AMEPAROMO is “the usual dosage for adults is 1500 mg (potency) of paromomycin sulfate administered orally after meals, divided into 3 doses per day for 10 days”, overdose present was defined as “daily total dose exceeded 1500 mg on at least 1 day, or the duration of treatment is 12 days or more”. Only dose per single dose, number of doses, start day, and end day are collected as records on treatment with AMEPAROMO in the CRF. If AMEPAROMO is taken a total of 30 times in 10 days and the initial dose on the start day (Day 1) is given after lunch or supper, the last dose on the last day (Day 11) will be after breakfast or lunch. Because the duration of treatment from the start day to the end day is calculated to be 11 days in tabulation, the duration of treatment of 12 days or more was selected.

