7.2.6. Observation period

The observation period shall start on the day the treatment with AMEPAROMO begins (Day 1) and end on Day 10 during which patient background information, records on AMEPAROMO treatment, records on concomitant therapies, and records on the treatment status and discontinuation of AMEPAROMO shall be entered in CRFs. When the treatment is discontinued during the observation period, the observation period shall be until the day when AMEPAROMO treatment is discontinued.

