7.3.3. Concomitant therapy

7.3.3.1. Drug therapy

Input the following information on all drugs used during the observation period. If adverse events (AEs) occurred, drugs administered for the treatment of AEs will be also entered:

- [1] Name of drug (product name)
- [2] Route of administration
- [3] Treatment period
- [4] Presence or absence of treatment for AEs

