8.2.3.4. Subgroup Analysis

To evaluate the relationship between patient background factors and the development of adverse drug reactions, risk ratio and risk difference between subgroups will be calculated for the incidence of adverse drug reactions in accordance with Section 8.1.3. For subgroups with risk ratio ≥ 2 or ≤ 0.5 , the number and proportion of patients who experienced adverse drug reaction will be summarized for each factor, using SOCs and PTs.

In addition, the number and proportion of patients who experienced adverse drug reaction will be tabulated by SOC and PT for each of the following factors.

- Age [elderly (≥ 65 years), non-elderly (< 65 years)]
- Hepatic dysfunction [absent, present]
- Renal dysfunction [absent, present]
- HIV infection [absent, present]

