8.2.3.5. Exploratory Analysis

The following exploratory analysis will be performed for factors affecting safety:

- For adverse drug reactions with high incidence ($> 10\%$), factors for development of adverse drug reactions will be examined using methods such as logistic regression analysis.
- To examine the effects of concomitant medications on development of adverse drug reactions, the number and proportion of patients by name of concomitant drug^c (drug subclassification and nonproprietary name) will be calculated by presence or absence of adverse drug reactions.

Additional exploratory analysis may be performed, as necessary. Among those exploratory analyses, only those that resulted in important interpretations will be reported.

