8.2.4.2. Clinical Response Rate (assessed by the investigator)

In the clinical response analysis set, the number and proportion of patients in whom the clinical response (assessed by the investigator) after AMEPAROMO treatment is effective will be

^c: The presence or absence of concomitant medications will be determined by excluding concomitant medications started to be used after the day of onset of the last adverse drug reaction observed during the observation period plus 28 days.

calculated as the clinical response rate. The 95% confidence interval of the AMEPAROMO rate will be calculated. The clinical response rate will be calculated using the following equation:

$$\text{Clinical Response rate (\%)} = \frac{\text{Number of patients with "effective"}}{\text{Number of patients in the clinical response analysis set excluding "indeterminate"}} \times 100$$

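### The concomitant-medication factor in SAP 5.3 is defined by the date of the ADR it is meant to explain, so its exploratory RR and RD can be biased with no drug effect; net direction and size are unknown (minor)

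*SAP*

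**What the plan says.** SAP 5.3 lists concomitant medication up to the development of ADRs, absent or present, as one of 13 background factors for the safety subgroup analyses. Footnote a decides presence by "excluding concomitant medications started to be used after the day of onset of the last adverse drug reaction" within the observation period plus 28 days. The footnote to 8.2.3.5, printed on the page with 8.2.4.2, repeats the rule: "The presence or absence of concomitant medications will be determined by excluding concomitant medications started to be used after the day of onset".

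The definition is used twice:

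- SAP 8.2.3.4: "risk ratio and risk difference between subgroups will be calculated for the incidence of adverse drug reactions". If RR is at least 2 or at most 0.5, tables by SOC and PT are added.
- SAP 8.2.3.5: a table by drug name, split by presence or absence of an ADR. Its stated purpose is "To examine the effects of concomitant medications on development of adverse drug reactions".

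On the reference group, SAP 5.3 says "Underlined categories will be used as a reference in comparisons between subgroups". The underlining is lost in the text available to me, so I take absent as the reference.

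Protocol 7.3.3.1 collects all drugs used in the observation period and adds: "If adverse events (AEs) occurred, drugs administered for the treatment of AEs will be also entered". It also collects a flag for each drug: "Presence or absence of treatment for AEs". Neither SAP footnote uses that flag.

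**The concern.** Exposure is classified with the help of the outcome, in two ways.

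1. **Truncation.** A patient with an ADR can become exposed only up to the last onset day. A patient without one has no stated cut-off. With absent as reference, this pulls RR below 1.
2. **Treatment drugs counted as exposure.** Only starts after the last onset day are dropped. A drug started on that day, or between a first and a last ADR, to treat a reaction still makes the patient exposed. This pushes RR above 1.

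With present as reference, both directions swap. At stake are the RR and RD for this factor, whether the 2 / 0.5 trigger fires, and the by-drug table, where a remedy for an ADR can look like a contributor to it. The third study objective asks about factors that may affect safety, and this factor bears on it directly.

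**Working it through.** The plan gives no figure to reproduce and none of the rates needed. N = 100 is a feasibility choice. The rates below are assumptions chosen to show the mechanism.

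**Inputs (assumed).** On a drug at Day 1: b = 0.40. Share of the rest who start one, uniformly over 10 days: s = 0.30. ADR incidence: p = 0.20. One ADR per patient, onset uniform over the same 10 days. Share of ADR patients given a new drug on the onset day: t. Drugs have no effect, so true RR = 1 and RD = 0.

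**Exposure under footnote a.**

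- No ADR: eN = b + (1−b)s = 0.40 + 0.60 × 0.30 = 0.58.
- ADR, no treatment drug: the chance that a start falls on or before onset is 0.5, so 0.40 + 0.18 × 0.5 = 0.49.
- ADR, with treatment drugs: eA = 0.49 + 0.51t.

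**Risks.** Present: p·eA / [p·eA + (1−p)·eN]. Absent: p(1−eA) / [p(1−eA) + (1−p)(1−eN)].

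At t = 0: 0.098/(0.098 + 0.464) = 0.174 and 0.102/(0.102 + 0.336) = 0.233, so RR = 0.75.

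| t | eA | Risk, present | Risk, absent | RR | RD (points) |
|---|---|---|---|---|---|
| 0 | 0.490 | 0.174 | 0.233 | 0.75 | −5.8 |
| 10% | 0.541 | 0.189 | 0.215 | 0.88 | −2.5 |
| 25% | 0.617 | 0.210 | 0.185 | 1.13 | +2.5 |
| 50% | 0.745 | 0.243 | 0.132 | 1.84 | +11.1 |

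The effects cancel when eA = eN, at t = 0.09/0.51 = 18%. With present as reference the four RRs become 1.34, 1.13, 0.88 and 0.54.

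**Drugs given between two ADRs.** Suppose 30% of ADR patients have two ADRs, half of these receive a drug in between, and t = 0. The last onset is the later of two, so the chance that a start precedes it is 2/3 and exposure before treatment is 0.40 + 0.18 × 2/3 = 0.52. Then eA = 0.7 × 0.49 + 0.3 × (0.52 + 0.48 × 0.5) = 0.571 and RR = 0.97, against 0.77 with none given.

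**Wider range.** A second calculation used p from 0.1 to 0.3, b from 0.3 to 0.7, s from 0.2 to 0.6, t from 0 to 0.5 and up to 20% of ADR patients treated for an earlier ADR (108 combinations). RR ran from 0.45 (p = 0.1, eA = 0.51, eN = 0.72: 0.073/0.163) to 3.34 (p = 0.1, eA = 0.748, eN = 0.44: 0.159/0.048, before rounding). Of the 108, 2 gave RR ≤0.5 and 16 gave RR ≥2.

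**When the bias shrinks or vanishes.** If untreated ADRs spread evenly to Day 38 while drugs start within 10 days, the chance that a start precedes onset is 1 − 5/38 = 0.868, eA = 0.556 and RR = 0.93. If all drugs are in use at Day 1 and none treats an ADR, eA = eN and RR = 1.00.

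**Trigger.** I simulated 40,000 null studies of 100 patients per case with the first set of inputs, applying the fewer-than-10 rule.

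| Rule | RR ≤0.5 | RR ≥2 |
|---|---|---|
| Footnote a, t = 0 | 17% | 1% |
| Footnote a, t = 50% | about 0.1% | 45% |
| Drugs in use on Day 1 | about 7% | about 5% |

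At 5% incidence with untreated ADRs, the trigger fires in 51.4% of null studies under footnote a and 48.4% under a Day-1 rule.

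**The case against.** The cut-off is a deliberate guard: a drug started after the last ADR cannot have caused it, and the factor's name says it covers drugs up to the reaction. SAP 4.1 calls the tests exploratory, 4.2 has no decision rules, and the trigger only adds tables. SAP 8.1.3 suppresses RR and RD for groups under 10. All ADRs are tabulated by SOC and PT anyway (8.2.3.1), concomitant medication is tabulated without this rule in 8.2.2, and Section 9 plans listings of ADRs and of concomitant drugs by patient. At low incidence, chance drives the trigger under either rule.

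All of that holds and keeps the point minor. It does not rescue the definition. The guard removes only later starts, and by shortening the window in ADR patients alone it creates the truncation. Listings let a reader check single cases but do not correct the RR or RD.

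Not all the truncation need come from the footnote. Protocol 7.2.6 says "The observation period shall start on the day the treatment with AMEPAROMO begins (Day 1) and end on Day 10", but also ends observation when treatment is discontinued. For an ADR patient who stops on the onset day, later drugs not given for an AE are not requested at all. My model gives every ADR patient the full 10 days.

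Three stronger readings are tempting, and the documents do not support them:

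- **That the bias has a known sign.** This needs drug-start and ADR-treatment rates, which are not given.
- **That for ADRs after Day 10 only treatment drugs matter.** Drugs for unrelated AEs still count without a cut-off in patients without an ADR. If 10% of those patients receive one, and no ADR patient does by the last onset, eN = 0.58 + 0.42 × 0.1 = 0.622 against eA = 0.58, and RR = 0.189/0.217 = 0.87. SAP 8.2.3 also ends the observation period at end of treatment, not at Day 10.
- **That the safety conclusions are compromised.** ADR incidence does not use this definition.

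**Conclusion.** The concern holds as a minor fault in an exploratory analysis. Read literally, footnote a lets the outcome decide part of the exposure, so RR and RD for this factor can depart from 1 and 0 with no drug effect. That the rule does this follows from its wording. How much it matters here cannot be known from the documents: every RR above rests on assumed rates, the two effects can cancel, and the bias can be nil. The reach is the RR and RD for one factor, its 2 / 0.5 trigger and the by-drug table in 8.2.3.5. Main ADR incidence, cyst-negative proportion and clinical response are unaffected. If the sponsor intends a cut-off for patients without an ADR, it is not written.

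**What to change.** In both footnotes, define exposure by a rule that is identical for all patients and does not depend on whether or when an ADR occurred, and exclude drugs flagged in the CRF as treatment for an AE.

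The simplest form: concomitant medication is present if at least one drug not flagged as AE treatment was started on or before the AMEPAROMO start day and was in use on that day. Rename the factor to match. Show later-started drugs and AE-flagged drugs descriptively, without RR or RD, and separately in the 8.2.3.5 table. This form also avoids the loss of later drugs when observation ends at discontinuation.

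The Day-1 form is one option among several and asks a narrower question than the SAP does. To keep the question about drugs added during treatment, use a time-dependent analysis to first ADR onset instead. Excluding AE-flagged drugs alone is not enough: it removes the upward pull but leaves the truncation (RR 0.75 at any t with the first set of inputs).

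The cost is SAP wording and programming, since treatment period and the AE-treatment flag are already collected under Protocol 7.3.3.1. Under the Day-1 form, drugs added after Day 1 leave the RR and RD. At low ADR incidence the change will hardly alter how often the trigger fires by chance.

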6. ENDPOINTS AND COVARIATES

6.1. Safety Endpoints

- Adverse drug reactions: Adverse events determined to be related to AMEPAROMO by the investigator
- Adverse events: All-causality adverse events
- Serious adverse events or reactions: Adverse events or adverse drug reactions in which the seriousness was determined to be serious by the investigator

6.2. Effectiveness Endpoints

- Proportion of cyst negative:

Results in patients who underwent the examination of cysts after AMEPAROMO treatment

- Cyst negative
- Cyst positive
- Indeterminate

- Clinical Response (assessed by the investigator)

On the day of completion of the observation period (or the day of completion of the study), the clinical response of AMEPAROMO should be comprehensively assessed based on the course of the general condition, laboratory findings and other relevant data after the start of AMEPAROMO treatment.

- Effective
- Not effective
- Indeterminate

6.3. Other Endpoints

Not applicable.

6.4. Covariates

As for the safety and effectiveness of AMEPAROMO, there are no covariates identified from clinical study data thus far obtained or potential covariates.

7. HANDLING OF MISSING DATA

When the causal relationship of adverse events is missing, the data will be handled as “related” for counting. When the seriousness/outcome of adverse events and action taken with

AMEPAROMO for the adverse events are missing, the data will be handled as “unknown” for counting.

For effectiveness endpoints, missing data will not be imputed.

8. STATISTICAL METHODS AND STATISTICAL ANALYSIS

8.1. Statistical Methods

8.1.1. Analysis of Continuous Data

Summary statistics (number of patients, mean, standard deviation, median, maximum, and minimum) will be calculated.

8.1.2. Analysis of Categorical Data

The number of patients and proportion of each category will be calculated.

8.1.3. Analysis of Binary Data

The number of patients and proportion will be calculated. If the confidence interval of proportion is calculated, two-sided 95% confidence interval (exact method) will be calculated.

If the proportion is compared between subgroups, risk ratio and its 95% confidence interval, and risk difference and its 95% confidence interval will be calculated. If the number of patients in subgroups compared is less than 10, the number and proportion of patients will be calculated but risk ratio and its 95% confidence interval, and risk difference and its 95% confidence interval will not be calculated.

8.2. Statistical Analysis

8.2.1. Overview of Patients

- **Number of sites by establisher and number of patients**

In CRF-collected patients, the number and proportion of sites by establisher shown below and the number and proportion of patients will be calculated.

- University hospitals
- National hospitals established by the Ministry of Health, Labour and Welfare
- Prefectural and municipal hospitals
- Public organizations
- Hospitals other than the above four established by corporations and individuals
- General practitioners/clinics

In addition, the mean, minimum, and maximum will be calculated for the number of patients per site.

- **Dispositions of patients**

In patients who registered to the study, the number of registered patients, the number of completed patients, the number of patients included in the analysis of safety, and the number of patients included in the analysis of effectiveness will be tabulated. In addition, the number of patients excluded from the analysis of safety and effectiveness and the number of patients by reason for exclusion will be tabulated.

- **Listing of discontinuations and dropouts**

In the safety and effectiveness analysis sets, the number and proportion of discontinued patients will be tabulated. In addition, the number and proportion of patients by reason for discontinuation will be tabulated.

- **Listing of excluded patients**

The listing of reasons for exclusion in patients excluded from the analysis of safety and effectiveness will be prepared.

8.2.2. Patient Background and Treatment History of AMEPAROMO

- **Patient background**

In the safety and effectiveness analysis sets, the following patient background factors will be tabulated in accordance with Section 8.1.

- Sex [male, female]
- Age (continuous)
- Age group [<15 years, ≥15 to <65 years, ≥65 years]
- Inpatient/outpatient status at the first prescription [inpatient, outpatient]
- Body weight (continuous)
- Body Mass Index (continuous)
- Diagnostic name [intestinal amebiasis, others]
- Diagnostic name [details of others]
- Severity [mild, moderate, severe, unknown]
- Initial onset/recurrence [initial onset, recurrence]
- Hepatic dysfunction [absent, present]
- Renal dysfunction [absent, present]
- HIV infection [absent, present]
- Past medical history [absent, present]
- Concurrent illness [absent, present]
- Presence or absence of prior treatment for intestinal amebiasis [absent, present]
- Clinical response of prior treatment [effective, not effective, indeterminate]

In the safety analysis set, the number and proportion of the following patients will be tabulated by SOC and PT of MedDRA.

- Past medical history
- Concurrent illness

In the safety and effectiveness analysis sets, the number and proportion of the following patients will be tabulated.

- Presence or absence of concomitant medication [absent, present]
- Concomitant medication
- Concomitant non-drug therapy
- Prior medication for intestinal amebiasis
- Prior medication other than those for intestinal amebiasis

- **Status of treatment of AMEPAROMO**

In the safety analysis set, the following status of treatment of AMEPAROMO will be tabulated:

- Duration of treatment (continuous)
- Dose per single dose (continuous)
- Number of doses (continuous)
- Daily dose (continuous)
- Presence or absence of overdose^c [absent, present]

The duration of treatment is from the day of initial dose in the study to the last confirmed day of dosing including the treatment suspension period.

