7.3.4. Study discontinuation record

Whether or not AMEPAROMO treatment could be completed should be checked. If AMEPAROMO treatment could not be completed, the date of the final observation should be entered, and the main reason for discontinuation corresponding to the items below should be chosen and documented. If an AE is selected for the reason, detailed information should be recorded in the AE column.

- [Reason for discontinuation]
- Insufficient clinical response
 - AEs
 - Not making revisits
 - Hospital/department transfer
 - Others

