8.2.3. Safety Analysis

Safety will be analyzed using data collected during the observation period (from the start day of AMEPAROMO treatment to the end day of AMEPAROMO treatment) plus 28 days^d. All adverse events reported in the study will be included in listings.

^c: Because the dosage and administration of AMEPAROMO is “the usual dosage for adults is 1500 mg (potency) of paromomycin sulfate administered orally after meals, divided into 3 doses per day for 10 days”, overdose present was defined as “daily total dose exceeded 1500 mg on at least 1 day, or the duration of treatment is 12 days or more”. Only dose per single dose, number of doses, start day, and end day are collected as records on treatment with AMEPAROMO in the CRF. If AMEPAROMO is taken a total of 30 times in 10 days and the initial dose on the start day (Day 1) is given after lunch or supper, the last dose on the last day (Day 11) will be after breakfast or lunch. Because the duration of treatment from the start day to the end day is calculated to be 11 days in tabulation, the duration of treatment of 12 days or more was selected.

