8.2.3.1. Adverse Drug Reactions

- **All adverse drug reactions**

The number and proportion of patients with adverse drug reactions will be tabulated by SOC and PT.

- **Serious adverse drug reactions**

The number and proportion of patients with serious adverse drug reactions will be tabulated by SOC and PT.

- **Details of adverse drug reactions**

The number and proportion of patients with adverse drug reactions will be tabulated by SOC and PT for each of the following items.

- Seriousness [serious, non-serious]
- Expected/unexpected [expected, unexpected]
- Intervention [discontinuation, temporarily discontinued or dose reduced]
- Outcome [not recovered, recovered with sequela, recovering, resolved/recovered, unknown]

In addition, the number and proportion of patients with adverse drug reaction that meets all of the following items will be tabulated by SOC and PT:

- The seriousness was considered “non-serious”;
- The intervention was “discontinuation”, “temporary discontinued”, or “dose reduced”
- The outcome was “not recovered” or “recovered with sequela”.

If the same adverse drug reaction (the same PT) occurs more than once in the same patient, it will be handled as follows in the tabulation of the number of patients with events:

- Seriousness: If both serious and non-serious events are reported, “serious” will be adopted.
- Expected/unexpected: If both expected and unexpected events are reported, “unexpected” will be adopted.
- Number of days to onset: The number of days to the first event will be adopted.
- Intervention: If multiple types of action are reported, one of discontinuation, temporarily discontinued or dose reduced, or other (none, dose increased), in descending order of precedence, will be adopted.

^d: The collection period was specified as the observation period plus 28 days because the period of reporting of safety information collected using the NIS AE Report Form of the study is up to 28 days after the end day of treatment.

- Outcome: The outcome of the last occurring event will be used.

- **Time to adverse drug reaction**

The number of patients who experienced an adverse drug reaction will be tabulated by time to first development (<3 days, ≥ 3 to <7 days, ≥ 7 to <10 days, ≥ 10 days), by SOC and PT.

- **Details of serious adverse drug reactions**

The number and proportion of patients with serious adverse drug reactions will be tabulated by expected/unexpected status by SOC and PT.

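### The 12-day arm of the overdose flag counts paused days, so a patient can be labelled as overdose without any excess dosing; the effect is descriptive and minor

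*SAP*

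**What the plan says.** SAP 8.2.2 lists duration of treatment and presence or absence of overdose among the treatment-status items. It defines duration as running "from the day of initial dose in the study to the last confirmed day of dosing including the treatment suspension period". This is the only definition of treatment duration in the SAP.

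The overdose footnotes to SAP 5.3 and 8.2.3 are worded alike. Overdose is present if "daily total dose exceeded 1500 mg on at least 1 day, or the duration of treatment is 12 days or more". They explain the cut-off by a late first dose: 30 doses begun after lunch or supper on Day 1 finish on Day 11. "Because the duration of treatment from the start day to the end day is calculated to be 11 days in tabulation", the threshold was set one day higher.

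On the data available, the same footnotes state: "Only dose per single dose, number of doses, start day, and end day are collected as records on treatment with AMEPAROMO in the CRF". Protocol 7.3.2 records dose, daily frequency and treatment period. Protocol 7.3.4 asks about completion ("Whether or not AMEPAROMO treatment could be completed should be checked") but not about interruptions.

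The flag is used in three places: the SAP 8.2.2 tabulation, a one-category safety subgroup in SAP 5.3 ("overdose present"), and a listing in SAP 9.

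SAP 8.2.3.1 treats temporary discontinuation as a recordable action for an ADR. Its precedence rule reads: "If multiple types of action are reported, one of discontinuation, temporarily discontinued or dose reduced", then other actions.

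**The concern.** A span from first to last dosing day measures how long treatment was spread out, not how much drug was taken. For an uninterrupted course at three doses a day the two move together, so a span cut-off can stand in for excess dosing. Once paused days count, they separate: a pause lengthens the span without adding a dose. The footnotes' reasoning does not address this case.

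At stake is what the overdose group means. It may include patients who took the 30-dose course or less. Some of them may be there because an ADR led to the pause, so that membership depends partly on the outcome the group is meant to describe. The group may be small, in which case a few such patients could change how its safety reads in a periodic safety report or the reexamination documents.

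**Working it through.** **Inputs.** Three doses a day for 10 days, that is 30 doses, at 1500 mg a day (overdose footnotes, SAP 5.3 and 8.2.3). Duration as in SAP 8.2.2. Flag: any day above 1500 mg, or duration of 12 days or more. Target of 100 patients (Protocol 7.5.1). My assumption: a pause consists of full days without dosing, after which three doses a day resume.

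**Formula.** Let s be the start slot on Day 1 (0 breakfast, 1 lunch, 2 supper), n the doses taken and k the dose slots missed, with k = 3 per full paused day. Then

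last dosing day = floor((s + n − 1 + k)/3) + 1.

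As the first dose is on Day 1, this is also the duration.

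**The SAP's own figure.** With n = 30 and k = 0:
- breakfast: floor(29/3) + 1 = 10
- lunch: floor(30/3) + 1 = 11
- supper: floor(31/3) + 1 = 11

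This reproduces the 11 days in the footnotes. None of these courses is flagged.

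**The same 30 doses with a pause, never above 1500 mg a day.**

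| Start | 1 paused day (k = 3) | 2 paused days (k = 6) |
|---|---|---|
| Breakfast | floor(32/3) + 1 = 11, not flagged | floor(35/3) + 1 = 12, flagged |
| Lunch | floor(33/3) + 1 = 12, flagged | floor(36/3) + 1 = 13, flagged |
| Supper | floor(34/3) + 1 = 12, flagged | floor(37/3) + 1 = 13, flagged |

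**Fewer doses, breakfast start.** In each case s + n − 1 + k = 35, which gives Day 12 and a flag:
- 27 doses, 3 paused days: 26 + 9 = 35
- 24 doses, 4 paused days: 23 + 12 = 35
- 15 doses, 7 paused days: 14 + 21 = 35 (7,500 mg in total at 500 mg a dose, against 15,000 mg for 30 doses)

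**Who is not affected.** Patients who stop for good by Day 11, and patients who pause but finish by Day 11.

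**Size per patient.** One patient flagged only because of a pause adds 1/100 = 1.0 percentage point to the overdose proportion if all 100 are in the safety set. If the set held 50 (assumption), it adds 1/50 = 2.0 points. The documents give no frequency of pauses, so no total can be computed.

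**Check of the remedy.** Take the span minus full paused days, with the threshold of 12 unchanged (breakfast, lunch, supper start):
- 30 doses, 2 paused days: 10, 11, 11; no longer flagged
- 27 doses, 3 paused days: 9, 10, 10; no longer flagged
- 34 doses, 1 paused day: 12, 12, 12; still flagged

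Scattered missed doses are not cured. With a supper start, 30 doses and 2 single missed doses, floor((2 + 29 + 2)/3) + 1 = 12, and no full paused day can be subtracted.

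**The case against.** The strongest reply is that the plan is consistent and the choice is open to view. SAP 8.2.2 says plainly that pauses count, and the footnotes also work from start day to end day. The label text they cite includes a 10-day period, and their reasoning concerns 30 doses within that course, not 30 doses over any span. A broad flag that feeds a listing is defensible in descriptive surveillance, and elapsed time may be all that can be derived from the fields collected. SAP 8.2.3.1 also tabulates ADRs by action taken, which helps to expose interruptions. Most of this stands, and it limits the point. It does not remove the gap: nothing in the SAP says that a paused course is meant to count as overdose.

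Four stronger readings should be set aside.

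- A reader might infer that SAP 8.2.2 contradicts the footnotes. It does not; they share one elapsed-time definition.
- A reader might infer that the cut-off was meant to spare every 30-dose course. The footnotes deal only with a late first dose.
- A reader might note that 33 uninterrupted doses from a breakfast start end on Day 11 unflagged, and conclude that pauses make the flag run against exposure. That case comes from the one-day tolerance. It has nothing to do with suspension, and the remedy leaves it unchanged.
- A reader might infer a distorted risk ratio. SAP 8.2.3.4 plans risk ratios for patient background factors, while overdose is listed in SAP 5.3 among the other factors, with a single category and no comparator.

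The end of observation on Day 10 in Protocol 7.2.6 does not dispose of the point. The flag presupposes that later end days are recorded, and SAP 8.2.3 runs the observation period to the end of treatment.

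**Conclusion.** The point holds in a limited, descriptive form and is minor. As written, the duration arm can mark a patient as overdose who took 30 or fewer doses and never exceeded 1500 mg in a day, provided the patient paused, resumed and took the last dose on Day 12 or later. An ADR could be the cause of such a pause. That route is possible on the text, but no passage shows how often pauses occur or whether paused doses are made up.

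The number of patients affected, and the direction of any effect on the group's ADR incidence, are unknown. The study is not confirmatory (SAP 4.1) and has no decision rule (SAP 4.2), so no inference turns on the flag. The arithmetic rests on full-day pauses and three doses a day on dosing days. No view is taken on what clinically counts as an overdose.

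**What to change.** Keep the SAP's thresholds, and keep elapsed duration as a descriptive item in SAP 8.2.2. Then:

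1. In both overdose footnotes, state whether suspension days count. For the duration arm of the flag only, subtract them where the dosing records show them.
2. In all cases, report the overdose count and the ADR incidence split by arm met: daily dose above 1500 mg, or duration only.
3. Mark known interruptions in the overdose listing.
4. State that, where pause dates are not recorded, the duration-only group can mix paused courses with genuinely long ones.
5. Do not move patients out of the group on the basis of the action-taken field. That field is tied to adverse events, so using it would make membership depend on the outcome in a new way.

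The cost is a few lines of SAP text, a small derivation, one extra split in a table and possibly some queries. The limits should be stated too. No passage lists suspension dates as collected, so the subtraction may have nothing to act on in some or all patients; the split by arm is then the only safeguard. It shows how many patients rest on duration alone, but cannot say which of them paused. Unrecorded pauses and scattered missed doses remain undetected.
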